#### **2.4. Procedure**

First, the permission from the instruments used in the study was obtained. Recruitment of participants was conducted by one of the study researchers who supervised the intervention delivery after obtaining approval from the hospital administrators to conduct the study. The list of all hemodialysis patients' names for both male and female floors, including their personal information (age, contact number, dialysis unit/room, hemodialysis shifts/days, hemodialysis access, hemodialysis starting date, and other chronic diseases) were gathered from the selected dialysis center. After that, all participants' files were checked for the last month Kt/V scores to conduct the inclusion criteria and select the study sample. The study purposes and protocol were explained to the patients in detail. Patients who agreed to participate in the study and met the eligibility criteria were asked to sign a consent form. Participants then completed the study variables' baseline measurements (T0) using the self-report questionnaires and measurements with a research assistant with a bachelor's nursing degree and 10 years of nephrology nursing experience. Another study researcher with a PhD degree, who was not involved in the recruitment process and data collection, randomized the participants to the experimental group ( $n = 34$ ) or the control group ( $n = 34$ ), using a simple 1:1 computer-generated sequence. The study variables were measured four weeks post the

start of the intervention (immediately after the twelve session, T1) and at the end of the final session (T2) for both groups. The measurements of the study variables at T0, T1 and T2 were conducted by the same research assistant who was not involved in any other parts of the study and blinded to randomization allocation. All measurements were privately taken at the dialysis center.

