## **2. Method**

### **2.1. Design**

This study used a repeated-measures, randomized, parallel control design and was conducted between September 2024 and February 2025 in the dialysis center at Jahra Hospital, Kuwait. The recruitment took approximately ten weeks, and the data collection and intervention took approximately nine weeks. Fifty-six ESRD patients undergoing hemodialysis were recruited using simple random sampling. Jahra Hospital is a governmental hospital with one of the biggest dialysis centers in Kuwait, with a female ward, male ward, and isolation ward. The center holds 70 dialysis machines/beds, with an average of 30 patients managed daily. The location was chosen because of its capacity to supply an adequate number of participants for the planned research. So, the researcher discovered that conducting an interventional study by enrolling patients from multiple Kuwait hospitals was costly and required a significant amount of time. Additionally, the researcher focusing on evaluating the efficacy of this treatment for ESRD patients receiving hemodialysis in Kuwait should prioritize addressing factors impacting internal validity over those impacting external validity or generalizability. Choosing a homogenous sample from a single setting is a method that can be used to enhance internal validity (51).

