#### **2.2.4. Biomedical markers**

The Access Cortisol Assay-33600 and CRP Reagent-447280 protocols, which involved blood sampling, were strictly followed. The Access Cortisol Assay is a paramagnetic particle, competitive binding immuno-enzymatic assay for the quantitative determination of cortisol levels in human serum, plasma (heparin, EDTA), and urine using the Access Immunoassay Systems, aiding in the diagnosis of adrenal-related disorders (59). The CRP reagent, in conjunction with IMMAGE Immunochemistry Systems, is intended for the quantitative determination of C-reactive protein (CRP) in human serum or plasma (heparin, EDTA), aiding in the evaluation of stress, trauma, infection, inflammation, and surgery (60).

Both protocols were precise, specific, and sensitive in accurately measuring serum cortisol and C-reactive protein concentration (59, 60). It is necessary to do the serum cortisol test multiple times a day or several days (61). However, it is important to carefully consider the timing of cortisol testing because it follows a strong circadian rhythm, peaking during the first hour after waking up and decreasing throughout the day until midnight. Hence, routinely checking serum cortisol levels during the first hour after waking up is viewed as a consistent and trustworthy biological indicator (61-63).

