### **2.3.2. Control group**

The participants in the control group were instructed to sit with their eyes closed and relaxed for 30 min three times a week for eight weeks during hemodialysis sessions to control for the nonspecific effects of social interaction and environment (Rausch et al., 2006). The timings of the control group sessions were similar to those of the experimental group, whereby if a given experimental group intervention lasted for 30 min, the control group participants would also be asked to sit with their eyes closed and relax for 30 min.

To avoid contamination bias, the experimental group participants were instructed to refrain from discussing any details about the intervention with anyone else throughout the duration of the study. The nurses and doctors at the hemodialysis center were not informed about the experimental group's intervention to avoid sharing details with the control group participants. During the study, the control group participants were given a placebo intervention, which involved closing their eyes and relaxing for 30 minutes. The experimental group participants' hemodialysis sessions were rescheduled to different units from the control group for eight weeks to prevent contamination bias during the intervention period. The participants from the experimental and control groups were allocated to separate hemodialysis units within the hemodialysis treatment center. Approval was obtained from the participants before managing the rescheduling with the nurses and physicians at the hemodialysis

center. The privacy and confidentiality of the participants were upheld by ensuring that no one could observe the data collection and intervention sessions through the use of curtains around each participant. At the end of the intervention, the researcher overseeing the intervention delivery confirmed with the control group participants that they had not engaged in or been provided with any information on mindfulness meditation throughout the study.

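### The simple 1:1 sequence leaves sex/ward and dialysis shift to chance, the stated model includes neither, and the text does not say whether the 34 + 34 arm sizes were fixed

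*Protocol*

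**What the plan says.** Section 2.4 of the Protocol has a researcher outside recruitment and data collection allocate 34 patients to each arm "using a simple 1:1 computer-generated sequence". No block, stratum or minimisation factor is named anywhere in the document.

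Section 2.1 describes a dialysis centre "with a female ward, male ward, and isolation ward". Section 2.4 states what was gathered at recruitment: "The list of all hemodialysis patients' names for both male and female floors", together with, among other items, "dialysis unit/room, hemodialysis shifts/days". Floor and shift were therefore in hand before consent, baseline measurement and randomisation.

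Section 2.3.2 adds that after allocation the experimental patients were rescheduled: "The participants from the experimental and control groups were allocated to separate hemodialysis units within the hemodialysis treatment center".

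Section 2.5 compares the arms on demographic and baseline variables with t and chi-square tests, then runs a mixed-design repeated-measures ANOVA. It states no term for ward, sex or shift.

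**The concern.** Two things stand out.

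- **Method and arm sizes.** A simple sequence, read as independent coin tosses, does not fix the size of either arm, yet section 2.4 reports two equal arms without comment. A reader cannot tell whether the total was fixed, blocks were used, or the equality arose by chance.
- **Unused information.** The centre is organised by sex-specific ward and by shift, and both were known for every patient. With 56 to 68 patients (sections 2.1 and 2.4 differ on the number), chance differences in such factors are common. Where a factor is related to an outcome, imbalance adds noise to the treatment comparison and makes a small trial harder to defend. The baseline tests in section 2.5 can show an imbalance but do not correct for it.

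At stake are precision and credibility. The validity of the comparison does not depend on stratification.

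**Working it through.** **Inputs from the Protocol.** Arms of 34 and 34, total 68 (section 2.4); 56 recruited (section 2.1); a simple 1:1 sequence (section 2.4). Both totals are used below because the document gives both.

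**Assumed input.** The share of patients holding a factor (for example, male ward or a given shift). The Protocol gives none, so 50% is the base case and 30% to 70% the range.

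**1. How often does unrestricted randomisation give equal arms?** With X ~ Binomial(n, 0.5):

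- n = 68: P(34:34) = C(68,34)/2^68 = 0.096.
- n = 56: P(28:28) = C(56,28)/2^56 = 0.106.
- n = 68: P(38:30 or more unequal) = 0.396.

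An exact split is uncommon, at about 1 in 10, but it is still the single most likely outcome.

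**2. What would unequal arms cost?** The variance of a difference in means is proportional to 1/n1 + 1/n2. Relative to 34:34, where the sum is 2/34 = 0.0588:

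- 38:30: (1/38 + 1/30)/(2/34) = 1.014, an increase of 1.4%.
- 40:28: (1/40 + 1/28)/(2/34) = 1.032, an increase of 3.2%.

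Arm size itself therefore matters little.

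**3. How often does a known factor end up unbalanced?** Take equal arms of size h = n/2 as given. If M of the n patients hold the factor, the number x in one arm is hypergeometric(n, M, h). The difference in shares between arms is |x − (M − x)|/h = |2x − M|/h.

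Base case, M = n/2:

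| n | P(difference at least 10 points) | P(difference at least 15 points) |
|---|---|---|
| 68 | 0.467 | 0.225 |
| 56 | 0.423 | 0.181 |

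Counts are whole patients, so the 15-point cut-off is met first by a difference of 6 patients. That is 6/34 = 17.6 points at n = 68 and 6/28 = 21.4 points at n = 56. The two probabilities are therefore not for quite the same size of imbalance.

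Across the assumed shares computed (30%, 50%, 60% and 70%), P(at least 15 points) runs from 0.136 to 0.225 at n = 68 and from 0.171 to 0.245 at n = 56. The message does not hinge on 50%.

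**4. What would blocks within ward do?** If the varying block sizes were, for example, 4 and 6, the worst unfinished block leaves a difference of 3 patients in a ward. On 34 per arm that is 3/34 = 8.8 points, which is half the 17.6 points of step 3.

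**The case against.** The other side has a strong case, and most of it stands.

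- **Unstratified randomisation is valid.** It neither biases the estimate nor inflates the type I error. This stands, and limits the point to balance and precision.
- **The equal split is no contradiction.** A reader might infer that either the method or the arm sizes must be misdescribed. The document does not support that. An event of about 10% can happen, and simple may only mean no strata and no blocks. A computer-generated half-split of a list of 68 consented patients would be 1:1, unstratified and exactly equal. What remains is an ambiguity that one sentence would resolve.
- **Shift and cortisol.** A reader might infer that an imbalance in shift would distort cortisol, since section 2.2.4 says that "it follows a strong circadian rhythm". That section goes on to favour sampling in the first hour after waking, which ties timing to waking and not to shift. Section 2.4 sits uneasily with this, because it places the follow-up measurements at the end of sessions at the centre. That is a separate matter of sampling time. The Protocol does not say that shift affects cortisol or sleep, so shift is a plausible factor to adjust for and not an established source of error.
- **Units.** A reader might infer that stratifying would cure the separation of the arms into different units. It would not: unit during treatment differs by arm by design. Nor does the text say how the units relate to the wards, and a patient's usual shift may not be the shift attended during the trial.
- **Partial protection already exists.** Gender is recorded and baseline comparability is examined. Because the repeated-measures analysis includes baseline, the group-by-time test is largely insensitive to stable level differences by sex or ward. A statistical analysis plan that is not available here may also name covariates. This reduces the stakes, but the model as stated includes neither factor.
- **Stratified blocks do not guarantee 34:34,** because the last block in each stratum may be incomplete. This is true, and equality of the arms is not the reason for the change.

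**Conclusion.** The point holds as an inexpensive improvement and a request for clarification, not as an error that invalidates the design. Section 2.4 should say whether arm sizes were restricted, since unrestricted allocation of 68 gives the reported split with probability 0.096. Sex/ward and shift were known beforehand, were left to chance, and do not appear in the stated model.

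Given equal arms and an assumed 50% share, a difference of 15 points or more arises with probability 0.225 at 68 patients and 0.181 at 56. Over the assumed shares of 30% to 70%, the range across both totals is about 0.14 to 0.25. How far such an imbalance would move the treatment estimate cannot be computed, because the Protocol does not say how strongly ward or shift relates to the outcomes.

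**What to change.** - **Section 2.4, randomisation.** Replace the simple sequence with a computer-generated 1:1 permuted-block list with varying block sizes, stratified by ward (male/female), and state how isolation-ward patients are assigned to a stratum. The researcher who already randomises keeps the list. Shift is better left to the model, because crossing ward with shift risks thin strata at 56 to 68 patients.
- **Section 2.5, analysis.** Add ward/sex and usual shift, as recorded on the recruitment list, as factors in the repeated-measures model.
- **If allocation is already complete,** as the past tense suggests, a new list is no longer possible. State in section 2.4 what was actually done (coin-toss sequence, fixed total, or blocks) and make only the change to section 2.5, saying openly when the factors were added.

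The cost is a different list from the same kind of software, where that is still possible, and a few degrees of freedom in the model. The change does not touch the separation of the arms by dialysis unit in section 2.3.2, which needs to be acknowledged in its own right.

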## **2.5. Data analysis**

SPSS version 25 (SPSS Inc., Chicago, Illinois, USA) was used to analyze the collected data. Prior to the main analysis, outliers and missing data were examined and managed as appropriate. Then, the assumptions of the statistical tests used, normality using a histogram graph, homogeneity of variance, and sphericity were checked and managed as appropriate. Mauchly's test of sphericity is used to assess whether the assumption of sphericity has been violated. When Mauchly's test of sphericity was significant ( $P < 0.05$ ), the degrees of freedom were corrected using Greenhouse-Geisser or Huynh-Feldt estimates of sphericity. The comparability of the two groups was evaluated in terms of demographic characteristics and the baseline measurements of the dependent variables using a *t*-test and Chi-square based on the measurements of the dependent variables. The main analysis was conducted with repeated-measures ANOVA (mixed design: within and between groups). A *P*-value of 0.05 was set as the significance level for the main analysis tests.

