The inclusion criteria for participation in this study were being a patient with ESRD undergoing hemodialysis three times a week for a minimum of one year, being aged 18 years old or over, having a urea reduction rate greater than 65% or Kt/V greater than 1.2 in the past month, and possessing Arabic literacy skills. The exclusion criteria included being a patient with cognitive dysfunction or mental retardation, suffering from rheumatoid arthritis, using a hearing aid, regularly consuming psychopharmacological drugs to reduce stress and improve sleep, participating in other psychological therapies at the time, or had prior formal training in mindfulness methods or a current meditation practice. Criteria for exclusion were built based on the chronic condition of the participants' status, which would make participation in the mindfulness sessions and home practice of mindfulness meditation problematic or distressing. Having serious psychiatric conditions, receiving psychopharmacological drugs, participating in other psychological or mindfulness therapies, or having severe hearing impairment would potentially risk failure in the intervention or limit participation in the mindfulness sessions. Further, patients with rheumatoid arthritis may have an increased burden of both age-related and disease-related cognitive decline, and elevated C-reactive protein levels may indicate an inflammatory process in the body (52, 53). The trial is reported in accordance with the CONSORT guidelines.

The required sample size was calculated using G-power version 3.1. Given a mixed-design (within groups and between groups) repeated measures ANOVA, power of 0.95, moderate effect size of 0.25, and  $\alpha$  of 0.05, the required sample size was 44 subjects. A similar study reported an attrition rate of 60% (54). Considering an expected attrition rate of 60%, 24 subjects should be added. Thus, the final required sample size was 68 participants.

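### The main repeated-measures ANOVA has no baseline covariate; adjusting for the T0 value would make the group contrasts more precise at little cost, by an amount that depends on a correlation the protocol does not give

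*Protocol*

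**What the plan says.** Protocol section 2.5 (Data analysis) fixes the model: "The main analysis was conducted with repeated-measures ANOVA (mixed design: within and between groups". It lists no covariate. The one use it states for baseline outcome values is a check of balance: "The comparability of the two groups was evaluated in terms of demographic characteristics and the baseline measurements of the dependent variables".

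Section 2.4 (Procedure) says that consenting patients completed "baseline measurements (T0) using the self-report questionnaires and measurements with a research assistant", and describes randomisation after that. It then refers to "The measurements of the study variables at T0, T1 and T2", so the same variables are taken before randomisation, at four weeks and after the final session.

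Section 2.1 (Design) sizes the trial for a mixed-design repeated-measures ANOVA with effect size 0.25, α 0.05 and power 0.95: "the required sample size was 44 subjects" before the allowance for attrition. It gives neither the number of repeated measurements nor the correlation between them.

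**The concern.** A pre-randomisation value of each outcome is already in hand. If T0 enters as a level of the time factor, the group-by-time test uses it only through within-person change, which in effect fixes the slope of T2 on T0 at 1. When the correlation between visits is below 1 and the variances are equal, the best slope is smaller than 1, and subtracting the whole baseline adds noise. Estimating the slope removes that noise.

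What is at stake is precision, not bias. The sample is small (44 complete participants in the sizing), so a narrower interval could matter if the true effect is smaller than the one planned for.

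**Working it through.** **Inputs from the protocol.** Two groups, 1:1; α 0.05; power 0.95; f = 0.25; 44 before attrition (sections 2.1, 2.4 and 2.5). Section 2.2.3 quotes test-retest values for the Perceived Stress Scale of 0.85 (original) and 0.90 (Arabic), without the retest interval.

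**Assumed.** One correlation ρ between all visits, equal variances, and ρ = 0.3, 0.5 or 0.7.

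**1. Reproduce the 44.** For the within-between interaction, λ = f²·N·m/(1 − ρ), with m − 1 and (N − 2)(m − 1) degrees of freedom. With m = 3, ρ = 0.5 and N = 44, λ = 0.0625 × 44 × 3 / 0.5 = 16.5 on 2 and 84 df, and power is 0.956; N = 42 gives 0.946. So 44 is reproduced. It does not identify the design, because m = 2 with ρ = 0.6 and m = 4 with ρ = 0.4 also give 44.

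**2. Variance of the T2 group contrast**, in units of 2σ²/n per arm:
- T2 minus T0: 2(1 − ρ)
- T2 adjusted for T0: 1 − ρ²
- Ratio: (1 − ρ²)/[2(1 − ρ)] = (1 + ρ)/2, so the reduction is (1 − ρ)/2

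Estimating the slope costs a factor of about 1 + 1/(N − 4) = 1.025 at N = 44.

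| ρ | Ratio | Reduction | Net at N = 44 |
|---|---|---|---|
| 0.3 | 0.650 | 35% | 1 − 0.650 × 1.025 = 33% |
| 0.5 | 0.750 | 25% | 1 − 0.750 × 1.025 = 23% |
| 0.7 | 0.850 | 15% | 1 − 0.850 × 1.025 = 13% |
| 0.85 | 0.925 | 7.5% | 1 − 0.925 × 1.025 = 5% |
| 0.90 | 0.950 | 5% | 1 − 0.950 × 1.025 = 3% |

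Simulation with 22 per arm agrees to within about one percentage point.

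**3. The same gain in participants.** 44/0.65 = 68, 44/0.75 = 59 and 44/0.85 = 52. At ρ = 0.5, an adjusted contrast from 44 is about as precise as a change contrast from 59, before the small cost of the slope.

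**4. Power at the planned effect** (m = 3, ρ = 0.5). The squared deviations of the visit-specific group differences sum to 4·m·f² = 4 × 3 × 0.0625 = 0.75. For differences (0, d/2, d) the sum is d²/2, so d = 1.22 SD. For (0, d, d) it is 2d²/3, so d = 1.06 SD. Simulated power at N = 44 (20,000 replicates; ranges cover the two patterns):

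| Effect | Test | Without adjustment | Adjusted for T0 |
|---|---|---|---|
| As planned | 2 df | 0.955 | 0.987–0.993 |
| As planned | T2 only, 1 df | 0.93–0.98 | 0.975–0.995 |
| Half | 2 df | 0.41 | 0.52–0.55 |
| Half | T2 only, 1 df | 0.41–0.51 | 0.50–0.62 |

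The 2-df rows compare the group-by-time F test with a joint test of the adjusted T1 and T2 differences. The 1-df rows compare the change contrast with the adjusted T2 contrast. All tests held their type I error close to 0.05.

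**The case against.** **It is a preference, not an error.** A mixed-design ANOVA is standard and valid, and covariates are often left to the analysis plan. The first part stands: nothing here makes the stated analysis wrong. The second carries less weight, because the protocol names its main model and sizes the trial on it, so adding T0 is a specific change to a stated choice.

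**The percentages rest on an assumed ρ.** This stands. A reader might take 15% to 35% as the gain this trial would see, but the protocol gives no between-visit correlation. The only repeat-measurement correlations in it are the stress scale's 0.85 and 0.90. Correlations over four or eight weeks may be lower, but those values lie above the assumed range and imply a much smaller gain. One common ρ and equal variances for sleep, stress, cortisol and C-reactive protein is also a simplification.

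**The benefit is slight where the trial was planned.** This stands too: 2-df power goes from 0.955 to about 0.99. The larger gains arise at a smaller effect, which is a supposition. The protocol also does not single out T2 as the main contrast.

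**T0 may not be a level of the time factor.** A reader might infer from 44 that it must be; step 1 shows that 44 does not prove it. If only T1 and T2 were analysed, adjustment would still help: the comparison would be with an unadjusted T2 difference, and the large-sample reduction would be ρ² (9%, 25% and 49% at 0.3, 0.5 and 0.7).

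**The trial is over.** Section 2.1 says the study "was conducted between September 2024 and February 2025", and section 2.2.2 reports a reliability coefficient from the study's own sample. Some data had therefore been analysed when this text was written. This limits the status of any added model.

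**Conclusion.** The point holds as an optional improvement. With T0 as a level of time, which is likely but unstated, the ANOVA is valid and loses some precision against adjustment for T0. The loss in the T2 contrast is (1 − ρ)/2 of its variance: 15% to 35% for ρ from 0.7 to 0.3, and 5% to 8% for ρ from 0.90 to 0.85, less one to three percentage points at 44 participants. These figures assume equal variances and a common correlation; the protocol supplies neither.

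Two stronger readings are tempting and not supported. The first is that the stated ANOVA is biased or ignores baseline: under randomisation it is valid, and with T0 as a level it uses baseline through change. The second is that the trial is underpowered for want of adjustment: at the protocol's own effect size, power is already about 0.95.

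**What to change.** For each outcome, analyse T1 and T2 in a linear model for repeated measures with group, time, group-by-time, the T0 value of that outcome and T0-by-time. Report the adjusted group difference with its 95% CI. The T0-by-time term lets the slope differ between visits, since the correlation with T0 may weaken from T1 to T2.

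State in section 2.5 whether T0 is a level of the time factor in the existing ANOVA.

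If outcome data have already been seen, label the adjusted model post hoc and supportive, and report it beside the stated ANOVA without replacing it.

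The cost is one or two degrees of freedom, one extra model per outcome and a short paragraph of text. No new data are needed, and the software already named in section 2.5 can fit the model.
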